5.8. Interim Analysis

No formal interim analysis is planned for this study.

6. STUDY SUBJECTS AND EXPOSURE

6.1. Subjects Disposition

Subject disposition will be summarized descriptively. It will include tabulations of the number and percentage of subjects in the categories listed below.

- Number of subjects consented
- Number of subjects in the “specified population” (e.g., Safety population)
- Number (%) of subjects who completed the study
- Number (%) of subjects who discontinued study
- Primary reasons of discontinuation may include any of the following
 - Withdrawal of consent
 - Adverse events
 - Lack of efficacy
 - Noncompliance with study procedures
 - Lost to follow-up
 - Other

Inclusion and exclusion criteria met/not met and reasons for screen failures will be summarized in a separate table.

6.2. Protocol Deviations

A protocol deviation is defined as any change, divergence, or departure from the study design or procedures defined in the protocol. An important protocol deviation (IPD) is defined as a protocol deviation that might significantly affect the completeness, accuracy, and/or reliability of the study data or that might significantly affect a subject's rights, safety, or well-being.

Prior to the database lock, PDs recorded in the EDC will be reviewed for the determination of IPDs, these will be summarized descriptively and listed. Protocol deviations will be provided in subject data listings.

6.3. Demographic and Baseline Characteristics

The summaries of demographic data and baseline characteristics will be provided for the Safety Populations. Subject demographic data (age, age group, sex at birth, gender, ethnicity, race, marital status, dependents, residence status, residence duration, level of education, annual household income, student status, employment status [contracted status/not employed status], hours worked per day, hours worked per week, days worked per week, work schedule [same shift/rotating shifts/split shifts]) and baseline characteristics (body weight, height, AISRS, CGI-S, MADRS, HAM-A, PHQ-8, GAD-7, WPAI:SHP, PSQI, and BRIEF-A) will be summarized descriptively.

Baseline Characteristics per ASRSv1.1-SC: The following ASRS.v1.1-SC measures at baseline will be included in the Demography and Baseline Characteristics summary table by counts and percentages.

- Total ASRS Score ≥ 24
- ASRS Screener: ADHD Symptoms Present
- ADHD Presentation type (based on ASRS)
 - Hyperactive/Impulsive (HI) ADHD Presentation Type
 - Inattentive (IA) ADHD Presentation Type
 - Combined (HI and IA) ADHD Presentation Type
 - Neither (HI or IA) ADHD Presentation Type

The measures for the ASRS v1.1-SC baseline characteristics will be derived as follows:

Step 1: Transform Ratings for ASRS at Baseline (screening tele-visit):

For Items 1, 2, 3, 9, 12, 16, and 18, ratings of: “Sometimes”, “Often”, and “Very Often” are assigned a value of 1; “Never” and “Rarely” are assigned a value 0.

For Items 4, 5, 6, 7, 8, 10, 11, 13, 14, 15, and 17, ratings of: “Often” and “Very Often” are assigned a value of 1 “Never”, “Rarely”, and “Sometimes” are assigned a value of 0.

Step 2: Sum and generate categorical (count and frequencies) summary for the following:

ASRS Screener: ADHD Symptoms Present. Sum transformed items #s 1-6 (range 0-6); Score ≥ 4 is considered highly consistent with symptoms of ADHD present.

ADHD Presentation Type (based on ASRS):

- HI Subscale = Sum of 9 transformed items: #s 5, 6, 12, 13, 14, 15, 16, 17, 18 (range 0-9); Score ≥ 6 implies HI is present.
- IA Subscale = Sum of 9 transformed items: #s 1, 2, 3, 4, 7, 8, 9, 10, 11 (range 0-9); Score ≥ 6 implies: IA is present.
- Summarize number and percentage of subjects with:
 - HI ADHD Presentation Type only at Baseline (HI Score ≥ 6 and IA Score < 6)
 - IA ADHD Presentation Type only at Baseline (HI Score < 6 and IA Score ≥ 6)
 - Combined (HI and IA) ADHD Presentation Type at Baseline (HI Score ≥ 6 and IA Score ≥ 6)
 - Neither (HI or IA) present at Baseline (HI Score < 6 and IA Score < 6)

6.4. Medical History

Medical history will be coded using the Medical Dictionary for Regulatory Activities (MedDRA) version 27.0 or the available version at the time of database lock. The number and percent of subjects reporting various medical, family, and psychiatric histories, grouped by system organ class (SOC) and preferred term (PT), will be summarized descriptively for the Safety Population. The table will be sorted by descending frequency of SOC and then PT within SOC.

All medical and psychiatric history will be listed. Nicotine, caffeine, and cannabis/marijuana use and responses on the Reproductive Menstrual Cycle History Questionnaire will be summarized.

6.5. Prior and Concomitant Medication

Prior and concomitant medications will be coded using the World Health Organization Drug Dictionary (WHO DD) version Global September 2023, and will be summarized descriptively by

the fourth level anatomical therapeutic chemical (ATC) classification and Preferred Name (PN), if applicable, using counts and percentages for the Safety Population. ATC fourth (ATC4) level is for the chemical, pharmacological or therapeutic subgroup. If an ATC4 level classification is not available for a coded term, the lowest available ATC level code will be substituted.

Prior medications are defined as those taken prior to first dose of study medication. Concomitant medications are those taken on or after start of study medication.

If a medication starts prior to the first dose and continues after the first dose it will be considered both prior and concomitant. Prior and concomitant medications will also be listed.

6.6. Study Treatment Exposure and Compliance

Duration of exposure is defined as the total number of days a subject is exposed to any study medication and defined as:

Duration of Treatment Exposure = date of last dose – date of first dose + 1.

Duration of treatment exposure will be summarized using descriptive statistics and by duration category:

- 1 to <= 29 Days
- 30 to <= 64 Days
- 65 to <= 99 Days
- >=100 Days

Analysis of exposure will also be explored by presenting the exposure using the modal total daily dose (most frequent dose, that is a dose with the longest exposure) over the treatment period. If two or more doses have the same exposure days, the average will be taken. The modal dose will be categorized into the following dosing intervals/groups:

Low, Medium, and High (200 mg, 300 to 400 mg and 500 mg to 600 mg).

This analysis will be repeated by using the “last dose” that a subject was on prior to either completing or discontinuing the study.

The starting date for a new dose will be the date when a subject confirms the receiving of a new shipment of SM.

Compliance:

Percentage compliance will be calculated by the overall treatment period. Percentage compliance will be calculated using the following derivations.

- Total Dispensed Dosage (mg) = Sum of the # of Capsules Dispensed × Dose per Capsule (mg)
- Total Returned Dosage (mg) = Sum of the # of Capsules Returned × Dose per Capsule (mg)
- Total Missed or Lost Dosage (mg) = Sum of the # of Capsules Missed or Lost × Dose per Capsule (mg)
- Total Dose (mg) Taken = Total dispensed dosage (mg) – [Total returned dosage (mg) +

Total missed or lost dosage (mg)]

- Total Planned Dose (mg) = Sum of planned dose (mg) at each day

SM Compliance = [(Total dose taken (mg))/Total planned dose (mg)]×100%.

SM compliance will be summarized descriptively. SM compliance will also be categorized as <80%, 80 to 120%, and >120%. The number and percent of subjects in each compliance category will be summarized descriptively.

7. EFFICACY ANALYSES

All efficacy endpoints will be summarized descriptively using the FAS.

7.1. Primary Efficacy Analysis

[figure not shown]
The primary efficacy endpoint is CFB in AISRS Total score by visit. The observed and change from baseline in Total score will be summarized by study visit using descriptive statistics. A comparison of Week 14/EOS vs Baseline difference in CFB; a nominal p-value from one sample t-test and associated 95% CI will be presented.

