### 6.3 End of Study

During the Televisit #4 (Week 14/EOS), the following will be administered, obtained or collected by a qualified/trained rater ([Table 1](#); ClinRO efficacy assessments should not be administered if participant has not taken daily dose of Qelbree for >7 consecutive days prior):

- AISRS
- CGI-S
- CGI-C
- SIGMA

	Protocol 812P413	
	Page 27 of 61	Version 2.0

- SIGH-A
- C-SSRS '*Since Last Visit*' Version
- Review AEs
- Review Concomitant Medications
- Report systolic/diastolic blood pressure, pulse rate, and weight
- Report UPT results (FOCPs only)
- RMCH Questionnaire's Menstrual-Question #5 (FOCPs only)
- SM accountability; report the number of remaining capsules in bottle
- Schedule safety follow-up televisit

In addition, at Week 14/EOS, the participant will complete or report the following via the study mobile app (efficacy assessments should not be administered if participant has not taken daily dose of Qelbree for >7 consecutive days prior):

- SM administration mode/time query; report admin method and average admin time
- ASRSv1.1-SC
- PHQ-8
- GAD-7
- WPAI:SHP
- PSQI
- BRIEF-A

If participant discontinues early (Early-Termination), perform Week 14 assessments; however, ClinRO/PRO efficacy assessments should not be administered if participant has not taken daily dose of Qelbree for >7 consecutive days prior.

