## 9.2 Efficacy Assessments

### 9.2.1 Clinician-Rated Outcomes (ClinROs)

As outlined in [Section 6.1.2](#), once a diagnosis of ADHD is confirmed, all clinician-rated outcome assessments will be administered by trained central raters or psychiatric nurse practitioners for reliability of data captured. ClinRO efficacy assessments should not be administered if participant is discontinuing and has not taken daily dose of Qelbree for >7 consecutive days prior to televisit.

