3.6. Sample Size

Approximately 750 participants will be dosed in this study, to obtain 500 completed (through the end of Week 14 of treatment) participants, with an anticipated attrition rate of 33%. There is no consideration for power for the sample size determination in this decentralized, open label study.

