5.3. Analysis Populations

Safety Population: This includes all subjects who received at least one dose of Qelbree.

Full Analysis Set: This includes a subset of subjects in the Safety Population who have a valid AISRS at baseline (prior to first dose) and at least one valid AISRS post-baseline assessment.

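### The Week 14 AISRS change uses only available values with 33% planned attrition, and beyond early-termination mapping nothing addresses missing visits, so it may overstate improvement in the dosed population

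*SAP*

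**What the plan says.** - **Analysis.** SAP 7.1: "The observed and change from baseline in Total score will be summarized by study visit using descriptive statistics". For Week 14/EOS against baseline, "a nominal p-value from one sample t-test and associated 95% CI will be presented". SAP 7 applies this to the full analysis set.
- **Population.** SAP 5.3 limits that set to dosed participants with a valid baseline AISRS and "at least one valid AISRS post-baseline assessment".
- **Attrition.** SAP 3.6: "Approximately 750 participants will be dosed in this study, to obtain 500 completed (through the end of Week 14 of treatment) participants", at an expected loss of 33%. The same section adds: "There is no consideration for power for the sample size determination in this decentralized, open label study".
- **Missing data.** SAP 5.6.1 deals with missing items within a scale. SAP 5.7 sends an ET visit to the next scheduled visit. No other rule covers an absent visit.
- **After stopping drug.** Protocol 10.1 withdraws participants who choose to stop medication before Week 14. Protocol 10.2 asks for Week 14 procedures from those who discontinue, except those lost to follow-up.
- **Off-drug assessments.** Protocol 6.3, for Week 14: "ClinRO efficacy assessments should not be administered if participant has not taken daily dose of Qelbree for >7 consecutive days prior". It repeats the bar for ET. Protocol 9.2.1, for all clinician ratings: "ClinRO efficacy assessments should not be administered if participant is discontinuing and has not taken daily dose of Qelbree for >7" consecutive days.

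**The concern.** The primary objective concerns adults with ADHD and comorbid mood symptoms, yet the only AISRS estimate certain to carry a CI and p-value rests on those who still have a score at Week 14. About a third of those dosed are expected to leave, and lack of efficacy and adverse events are among the listed reasons. Week 4 and Week 9 scores from leavers are collected but do not inform the Week 14 estimate. If leavers did worse, the mean profile over Weeks 4, 9 and 14 would mix real change with the loss of poor responders, and the CI would give no sign of it.

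**Working it through.** **1. The plan's own figures.** 750 × (1 − 0.33) = 502.5 completers, and 500 / 0.67 = 746.3, so 747 dosed are needed. Both agree with 750 and 500. About 750 − 500 = 250 dosed participants do not complete.

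**2. Which leavers reach Week 14 under SAP 5.7.**

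| Time of leaving | With an ET AISRS | Without one |
|---|---|---|
| Before Week 4 | Counted at Week 4; absent at Week 14 | Not in the full analysis set |
| Weeks 4 to 9 | Counted at Week 9; absent at Week 14 | Absent at Week 14 |
| After Week 9 | Counted at Week 14 | Absent at Week 14 |

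An ET score will often be lacking for those lost to follow-up or more than 7 days off drug.

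**3. Size as a function of the unknown.** Overstatement = (share of dosed missing at Week 14) × (mean change in the missing − mean change reported). As an illustration, take the reported mean as −15.5 and the SD as 0.91 × √175 = 12.04, both from the 6-week adult trial summarised in Protocol 3.2.2. Using them at 14 weeks is an assumption. The CI half-width at n=500 is 1.96 × 12.04 / √500 = 1.06. With all 250 missing, the all-dosed mean is (500 × −15.5 + 250 × d) / 750:

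| Leavers' mean change d | All-dosed mean | Overstatement |
|---|---|---|
| 0 | −10.3 | 5.2 |
| −7.75 | −12.9 | 2.6 |
| −11.7 | −14.2 | 1.3 |
| −15.5 | −15.5 | 0 |
| −18 | −16.3 | −0.8 (understated) |

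The bias equals the half-width when leavers improved 3 × 1.06 = 3.2 points less than completers. If half the leavers had a score counted at Week 14 and d = 0, the reported mean would be (500 × −15.5 + 125 × 0) / 625 = −12.4, and the overstatement 12.4 − 10.3 = 2.1.

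**4. Simulation.** Every input is an assumption:

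- mean change −10, −13.5 and −15.5 at Weeks 4, 9 and 14; SD 12; between-visit correlation 0.6 to 0.75
- 11% lost at random before Week 4, then logistic dropout on the last observed change with slope 0.5 to 1.5 per SD, calibrated to 33% in total
- an ET score midway between that person's Week 9 and Week 14 values
- 400,000 simulated participants per scenario

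| Post-Week-9 leavers giving an ET score | Excess improvement at Week 14 (points) |
|---|---|
| None | 0.9 to 2.7 |
| Half | 0.5 to 1.9 |
| All | 0.2 to 1.2 |

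With no ET scores, slope 0 gives about zero, slope 0.25 about 0.5, and slope −0.25 reverses the sign.

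**5. The off-drug wording.** Protocol 6.2 governs Weeks 4 and 9 and bars the scales only when the participant is discontinuing and more than 7 days off drug. Protocol 9.2.1 says the same for clinician ratings in general. Protocol 6.3 drops the discontinuing condition at Week 14. Someone who lapses for more than 7 days but stays in the study is therefore rated at Week 14 under 9.2.1 and not rated under 6.3. The conflict is confined to that case.

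**The case against.** The study is single-arm, open-label and descriptive. It has no formal hypotheses (SAP 5.5), the p-value is nominal, and the endpoint is change by visit. The number of observations at each visit and the reasons for discontinuation will be reported, so attrition will be visible. All of this stands, and it lowers the severity. It does not remove the issue, because any bias lies in the mean itself.

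A reader might infer that the plan has no method at all for missing visits, or that Week 14 describes completers only. SAP 5.7 rules out both: some leavers after Week 9 enter Week 14, and some before Week 4 enter the full analysis set.

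A reader might also infer that the estimate does overstate improvement. The documents do not show that. They list possible reasons for leaving without frequencies. In the earlier adult trial about 9% of the drug arm stopped for an adverse reaction, against 1 − 267/372 = 28% non-completion over both arms, so other reasons may well predominate.

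Nor does a likelihood model restore the truth in general. It does so when dropout depends only on observed scores, and that was built into the simulation. Its target is change had participants continued, not outcome after stopping. Restricting scores to recent drug use can also be a legitimate on-treatment choice, provided it is stated.

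**Conclusion.** The concern holds as a gap in the plan, not as a demonstrated bias. The Week 14 estimate rests on available values with a third of participants expected to leave; ET mapping repairs this only in part, and no sensitivity analysis tests it. Overstatement is likely if poor responders leave more often. On the assumptions above it runs from 0.2 to 2.7 points depending on ET capture, so it may fall below or exceed the 1.06-point half-width. It is about zero if dropout is unrelated to response, and could reverse if good responders leave. Setting these figures against the 3.7-point drug-placebo difference from the earlier trial would not be apt, because this study has no comparator. Severity: should fix.

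**What to change.** 1. Keep the observed-value tables as the protocol's descriptive primary summary (Protocol 12.1 and 12.8.1).
2. Beside them, report the Week 14 least-squares mean change with 95% CI from a repeated-measures likelihood model. Use baseline, Week 4, Week 9 and Week 14 AISRS as responses, with unstructured covariance, in all dosed participants with a baseline AISRS. State that it assumes missing at random and targets change had participants continued.
3. Add one conservative sensitivity analysis, for example zero Week 14 change for those who leave because of an adverse event or lack of efficacy.
4. List the model in SAP 9, which now declares no changes from the protocol's analyses.
5. Reconcile the wording on more than 7 days off drug in Protocol 6.3 with that in 9.2.1, and state how any off-drug scores enter each analysis.

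The cost is SAP text, modest programming on data already collected, and a short protocol clarification. The downside is that the reported improvement may be somewhat smaller. If leavers resemble completers the estimates will agree, and the result will be easier to defend.

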7.2. Secondary Efficacy Analysis

The following secondary endpoints will be analyzed in a similar manner to the primary endpoint. A comparison of Week 14/EOS vs Baseline difference in CFB with a nominal p-value from one sample t-test and associated 95% CI for any of the secondary endpoints may be explored as needed.

- CFB in AISRS Inattention Subscale score by visit
- CFB in AISRS Hyperactivity/Impulsivity Subscale score by visit
- CFB in ASRSv1.1-SC Total score by visit
- CFB in ASRSv1.1-SC Inattention Subscale score by visit
- CFB in ASRSv1.1-SC Hyperactivity/Impulsivity Subscale score by visit
- CFB in CGI-S score by visit
- CGI-C score by visit
- CFB in MADRS Total Score at Week 14/EOS
- CFB in PHQ-8 Total Score by visit
- CFB in HAM-A Total Score at Week 14/EOS
- CFB in GAD-7 Total Score by visit
- CFB in the WPAI:SHP:
 - Absenteeism percentage by visit
 - Presenteeism percentage by visit
 - Work Productivity percentage by visit
 - Regular Activity percentage by visit
- CFB in BRIEF-A T-score at Week 14/EOS for the
 - GEC
 - BRI
 - MI
- CFB in PSQI global score at Week 14/EOS

7.3. Exploratory Efficacy Analysis

8. SAFETY ANALYSES

The assessment of overall safety and tolerability will be based on adverse events, vital signs (blood pressure, pulse rate, and weight) and C-SSRS.

All safety analyses will be performed using the safety population.

8.1. Adverse Events

All adverse events (AEs) will be coded using the MedDRA Version 27.0 or current version.

A treatment-emergent adverse event (TEAE) is defined as an AE with a start date on or after the first dose of study medication, or that worsened in severity following the first dose of study medication. Any event that is present at baseline but worsens in severity will be determined by the Investigator and entered in the eCRF as a new AE. Thus, AEs that occurred on or after the first dose of study medication are TEAEs.

The incidence of TEAEs (number and percent of subjects) will be summarized by System Organ Class (SOC), preferred term (PT), and treatment groups. It will be sorted by decreasing frequency for the overall active treatment groups. A subject with multiple occurrences of an AE with the same PT will be counted only once in the AE category per SOC and PT for summary tables. In addition, for TEAE tables that are summarized by PT and treatment group, the sorting will be based on the decreasing frequency within the PT.

Based on the investigator's determination, the severity of TEAEs will be classified as mild, moderate or severe. For summaries by severity, a patient experiencing multiple AEs in the same PT with different intensities will only be counted once with the maximum severity. If severity is missing, then the maximum severity will be assumed for the analysis (i.e., severity = severe).

The relationship between the study medication and a TEAE is determined by the investigator and will be classified as unrelated (i.e., unlikely related or not related) or related (possibly related, probably related or definitely related). TEAEs with missing relatedness will be counted as definitely related. For summaries by relationship, a patient experiencing multiple AEs in the same PT with different relationship will only be counted once with the most related occurrence.

An overview of TEAEs will include summaries of incidence rates of subjects who had at least one TEAE, serious TEAE, TEAE leading to death, TEAE by maximum severity, TEAE by relationship, TEAE leading to withdrawal of study medication and related serious TEAE.

In addition to the overview of TEAE summary, the following summary tables will be provided:

- Treatment-Emergent Adverse Events by System Organ Class and Preferred Term
- Most Common ($\geq 5\%$) Treatment-Emergent Adverse Events by Preferred Term
- Treatment-Emergent Adverse Events by System Organ Class, Preferred Term, and Maximum Severity
- Treatment-Emergent Adverse Events by System Organ Class, Preferred Term, and Relationship to Study Medication
- Serious Treatment-Emergent Adverse Events by System Organ Class and Preferred Term
- Treatment-Emergent Adverse Events Leading to Withdrawal of Study Medication by System Organ Class and Preferred Term

In addition, listings will be provided for TEAEs, SAEs, TEAEs Leading to Withdrawal of Study Medication, and Deaths. If no SAEs or Deaths occurred, a blank listing with “No SAE (or Deaths) were reported on this study” will be indicated in the listing.

8.2. Vital Signs

8.2.1. Absolute Value and Change from Baseline

Change from baseline in vital sign variables (blood pressure, pulse rate and weight) will be calculated for each post-dose visit.

Observed values and change from baseline will be summarized descriptively by visit.

8.2.2. Shift in Vital Signs

Compared to the reference range, each of the three vital signs variables (diastolic blood pressure, systolic blood pressure and pulse rate) values will be classified as low, normal, high or missing. Shift tables for the change from baseline to all study visits will be summarized using number and percentage of subjects by visit.

Vital sign normal ranges are presented in [Table 1](#).

Table 1. Vital Signs Normal Ranges

Parameter	Low	High
Diastolic blood pressure (mmHg)	60	90
Systolic blood pressure (mmHg)	90	140
Pulse rate	50	100

